5 STUDY POPULATION

5.1 Participant Inclusion Criteria

A **Patient** must meet all of the following criteria to be eligible to participate in the study:

- Be a patient being treated at the Rutgers School of Dental Medicine
- Be 18 years or older
- Be able to understand the informed consent.
- Provide signed and dated informed consent form
- Be able to understand all instructions for data collection instruments in English
- Be willing and able to comply with all study procedures, including having a COVID-19 test performed

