3 OBJECTIVES AND OUTCOME MEASURES

3.0 Rutgers Feasibility Study Outcomes

PILOT Objectives	Brief Description/Justification of Outcome Measure	Outcome Measured By	Time Frame
To Determine Patient Willingness to Participate	Willingness to participate is important in determining whether patients would be willing to participate in a large-scale study	Ratio of patients agreeing to participate as compared to all patients asked to participate Thoroughness of consent process and ability to ask questions	Willingness to Participate: Patients – at time of consent by patients Patients – at End-of-Study
To Determine Patient Willingness/Ability to Follow Thru with Triage, Testing and Survey Administration Procedures	Determining willingness and ability to follow thru with triage, testing and survey administration procedures is important for refining the survey procedures	% who complete the study % who complete surveys o Pre-Visit Patient Survey o End-of-Visit Patient Survey % who feel testing (Saliva procedure was easy to comply with o Specimen collection o Specimen preparation for shipping o Specimen storage o Timeliness of results o Reporting of results	% Complete Study: Patients – End-Of-Visit (Day 1) % All Surveys Completed: Patients – End-Of-Visit (Day 1) % Feel Testing Protocol was Easy to Comply With: Patients – End-Of-Visit (Day 1)
To Determine Ease of Use with REDCap Survey Instruments Patient Subject Start-of-Visit Survey End-of-Visit Survey Triage Survey	Determining the ease of use and completeness of the REDCap instruments enables refinement of the system	% who feel surveys are easy to complete due to administration method:	% indicating surveys were easy to complete due to administration method: • Patients – at end of patient visit % indicating survey questions were easy to understand: • Patients – End-Of-Visit (Day 1) % Surveys Completed: • Patients – End-Of-Visit (Day 1)

3.1 Primary Outcomes for Full Study (Data Collection is Being Performed to Determine Instrument Feasibility)

Full Study Objective	Brief Description/Justification of Outcome Measure	Outcome Measured By	Time Frame

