4 STUDY DESIGN

Description: This study will assess the feasibility of implementing one COVID-related testing procedure in the dental setting. Results from this study may provide preliminary data to inform a larger network-wide study grant application.

Study Population: The study population for this study will be patients seen at the Rutgers School of Dental Medicine.

Important Outcomes: For this study, important outcomes include percent of patients willing to participate and percent completing the protocol.

Single or Multicenter: Single- this study will utilize the Rutgers School of Dental Medicine's Newark facility.

Number of Study Groups/Arms: One (1)

Expected Duration of Subject Participation: Subjects will be actively participating in the study for 2 weeks.

Sequence of Procedures and Duration of Study Period: Consent Process

About two weeks prior to their scheduled dental visit, patients will be contacted by the dental office to determine their willingness to participate in the study. Patients who indicate interest will be sent an email link, which opens the consent. The consent will clearly outline participant expectations and offer the opportunity for potential participants to contact the office for more information as needed. Participants who fully understand the study and elect to participate will affirm their willingness to participate by clicking the "I agree to take part in this study" button at the end of the consent form. Once in the office to provide their saliva sample, patients will also be asked to provide signed informed consent.

Study Procedures

Study participants will be asked to do the following:

- Two weeks before the dental visit
 - o Complete an electronic survey: Patient Pre-Visit Survey
 - Questions explore perceptions of safety and comfort, reasons for delaying dental care, concerns about returning to dental care, safety precautions valued, importance of triage and testing, and demographics
 - Launched automatically after the completed consent
 - Receive a saliva collection kit by mail
- One week before the dental visit
 - o Complete a COVID-19 saliva test
 - Spit into a tube
 - Package as directed
 - Drop off the completed test kit at the dentist's office
- Day prior to the dental visit
 - Undergo a COVID-19 triage screening over the phone*
 - Screening includes symptom questions (presence or absence of):
 - fever or chills
 - cough
 - shortness of breath or difficulty breathing
 - fatigue
 - muscle and body aches

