6 STUDY SCHEDULE

6.1 Patient Subjects

The following is the schedule of events for patients participating in the study.

Visit	Day	LAB Subjects Activities Performed
2 Weeks Prior	Day -14 (+/- 7 days)	Potential subjects contacted to introduce and determine interest in the study Obtain electronic consent Complete Pre-Visit Patient Survey
1 Week Prior	Day -7 (+/- 5 days)	Obtain informed consent signatures Provide saliva specimen
Day Prior	Day -2 (+/- 3 days)	Perform Prior-Day Triage Survey Obtain test results and provide to patient subject
Visit	Day 1	Complete Start-of-Visit Survey Complete Start-of-Visit Triage Case Report (Provision of Dental Treatment - not part of research protocol) Complete End-of-Visit Survey Complete Patient Participation Questionnaire

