6.2 Withdrawal Visit

Not applicable. If a subject withdraws early, there is no withdrawal visit.

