7.1 Study Procedures/Evaluations

The following study procedures will be completed:

Patient Subjects - LAB Protocol

Procedure and Evaluations	Purpose	Completed as Part of Study	When Performed	How Completed
Obtain Informed Consent	Complete informed consent	Yes	2 Weeks Prior (day- 14 +/-7 days) 1 Week Prior (day-7 +/-5 days)	Electronic consent obtained prior to initiating Pre-Visit Patient Survey Electronic signatures collected via REDCap Informed Consent Form when saliva specimen brought to office
Triage Case Reports	Collect COVID-19 screening data	Yes	Day Prior (day -2 +/- 2 days) Visit (day 1)	Data entered into REDCap via eCRF by Clinical Director, co-investigator or study staff member who interviews subject
Testing Case Reports	Collect information on outcomes of COVID-19 testing		Day Prior (day -2 +/- 2 days	Saliva Viral SARS-CoV-2 test results entered into REDCap via eCRF by Research Clinical Director, coinvestigator or study staff member based on testing result report obtained from secure e-mail.
Start-of-Visit Patient Survey Safety and Comfort COVID-19 Testing Preferences Perception of Importance Medical history Likelihood to report COVID-19 symptoms	Collect outcome measures	Yes	Visit (day 1)	Data entered via REDCap self- administered survey.
Dental Procedures Performed	Maintain patient oral health	NO	Visit	Completed by Dental Health Care Workers
PPE observed in office Environmental controls observed in office	Collect outcome measures	Yes	Visit (day 1)	Data entered via REDCap self- administered survey.
Patient Participation Questionnaire	Collect feasibility information on surveys and logistics	Yes	End of Study (Day 28)	Data entered via REDCap self- administered survey.

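### Two consent steps and no stated point of entry: if the signature taken at saliva hand-in defines entry, patients who never return the kit leave the follow-through denominator

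*Combined protocol and SAP*

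**What the plan says.** **Signature as entry.** Section 5.1 requires every patient to meet all its criteria, one of which is "Provide signed and dated informed consent form". Three places put that signature at the specimen step:

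- Section 4: "Once in the office to provide their saliva sample, patients will also be asked to provide signed informed consent".
- Section 6.1, in the row for one week prior (Day -7 +/- 5 days): "Obtain informed consent signatures Provide saliva specimen".
- Section 7.1: "Electronic signatures collected via REDCap Informed Consent Form when saliva specimen brought to office".

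**E-consent as entry.** Section 4 says that participants who "elect to participate will affirm their willingness to participate by clicking the 'I agree to take part in this study' button" do so about two weeks before the visit. It then lists the Pre-Visit Survey and receipt of the mailed kit as tasks of study participants. Both come before any signature. Section 14.3 accepts electronic consent for the first survey and takes written consent on arrival at the clinic. Appendix A marks consent only in the two-weeks-prior column. Participation is stated to last two weeks.

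**Outcomes.** Section 3.0 lists, under willingness and ability to follow through with triage, testing and surveys, the percentage "who complete the study", without a denominator. Section 4 says "important outcomes include percent of patients willing to participate and percent completing the protocol". Section 11.3 plans frequencies and defines no analysis set. Section 5.3 sets a target of 20 without saying at which consent step they are counted.

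**The concern.** The second feasibility objective asks whether patients will carry through with triage, testing and surveys. Producing a saliva sample and bringing it to the office is a main added burden of the protocol, so patients may well be lost at that step. The signature sits at the same step. An entry rule based on it selects patients on having done what the study sets out to measure.

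A patient who clicks to agree, answers the survey and never returns the kit might then be counted as willing under the first objective and be absent from the second, without ever being recorded as a failure. The withdrawal rules in Section 5.4.2 do not settle it. They cover people who withdraw consent, not people who simply do not come back.

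Percent completing is one of two outcomes that Section 4 singles out, and the results may inform a larger network study. An undefined denominator can also be chosen after the data are seen.

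**Working it through.** **No figure to reproduce.** Section 11.2 states that no sample size calculation was done, and the documents give no kit-return or completion rate. The check therefore compares two denominators over assumed losses.

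**Step 1: what each entry rule does to a non-returner.**

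| Question | Entry at signature (5.1 with 4, 6.1, 7.1) | Entry at e-consent (4, 14.3, Appendix A) |
|---|---|---|
| Is a non-returner eligible? | No: never signed | Yes |
| Counted toward 20? | No | Yes |
| In the completion denominator? | No | Yes, as a non-completer |

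Section 5.1 also requires willingness and ability to comply with all procedures, including the test. That is a second ground on which a non-returner could be classed as ineligible.

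**Step 2: formulas.** Let E be the number who e-consent, R the number who return the kit and sign, and F the number who finish.

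- Specimen return among signers is R/R = 100%, unless someone signs without handing in a sample. Among e-consenters it is R/E.
- Completion among signers is F/R. Among e-consenters it is F/E = (R/E) x (F/R).
- The signed denominator therefore inflates completion by the factor E/R, whatever happens later.

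Intervals are exact (Clopper-Pearson) 95%.

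**Step 3: the 20 counted at e-consent (E = 20; R and F assumed).**

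| R | F | Return, R/E | Completion among signers, F/R | Completion among e-consenters, F/E |
|---|---|---|---|---|
| 20 | 18 | 100% (83.2-100) | 90% (68.3-98.8) | 90% (68.3-98.8) |
| 16 | 14 | 80% (56.3-94.3) | 87.5% (61.7-98.4) | 70% (45.7-88.1) |
| 14 | 12 | 70% (45.7-88.1) | 85.7% (57.2-98.2) | 60% (36.1-80.9) |
| 14 | 10 | 70% (45.7-88.1) | 71.4% (41.9-91.6) | 50% (27.2-72.8) |

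With R = 14, return among signers would be reported as 14/14 = 100% (76.8-100). In the third row the inflation is 20/14 = 1.43, and 0.70 x 0.857 = 0.60.

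**Step 4: the 20 counted at signature (R = 20; E assumed).** Return among signers is always 20/20 = 100% (83.2-100). Among e-consenters it is 20/25 = 80% (59.3-93.2), 20/28 = 71.4% (51.3-86.8) or 20/40 = 50% (33.8-66.2).

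**Step 5: the ease ratings.** Section 3.0 collects the ease-of-testing ratings at the end of the visit, and Section 6.2 says "If a subject withdraws early, there is no withdrawal visit". Patients who found the kit too hard to return are not asked, whichever consent step defines entry. Section 5.4.2 does have staff interview those who withdraw.

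**The case against.** A reader might infer that non-returners are not participants at all, and that follow-through is near 100% by construction. The documents do not support that as a statement of what the plan does.

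- **Entry is contradictory, not settled.** Section 4 calls people participants at the click, and the two-week participation period and Appendix A fit entry at Day -14. Section 3.0 also includes the Pre-Visit Survey, done before any signature, in its survey-completion outcome.
- **No signed-only analysis set is named.** Section 11.3 plans frequencies and stops there.
- **Non-returners might surface elsewhere.** Section 13 says that the share of incomplete surveys and forms will be analysed as an outcome, and Section 11.3 lists completeness of the Testing Case Report.
- **Completion can still fall after the signature.** A sample may be unprocessable (Section 7.2.1), a positive test or triage can stop the scheduled visit (Sections 4 and 7), a visit can be missed, and the end surveys can be left unfinished.
- **The size is assumed.** The exact intervals overlap widely, and no progression threshold depends on the figure.

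All of this stands, and it limits the point to a conditional one. It does not remove it. Neither Section 11.3 nor Section 13 sets a denominator that would bring non-returners back, and the one explicit eligibility list requires the signature.

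**Conclusion.** The concern holds conditionally. The protocol contradicts itself on which consent step is entry and leaves the follow-through denominators undefined. If the signature rule in Section 5.1 is followed, specimen return is about 100% regardless of the true rate, and study completion is overstated by the factor E/R. With the assumed 14 of 20 returning and 12 finishing, that is 86% against 60%. If every e-consenter returns the kit, the two denominators agree and nothing is lost.

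The kit-return rates are assumptions, shown here from 50% to 100%. With about 20 patients the figures are imprecise on either denominator, but the shift from dropping non-returners always favours the protocol and is not sampling error. This should be fixed before analysis. In a small descriptive study that may provide preliminary data, it does not threaten the study as a whole.

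**What to change.** 1. State in Sections 5.1, 3.0 and 11.3 that e-consent at Day -14 defines entry to the feasibility analysis and the count toward 20. Keep the written signature as a requirement before further procedures, as in Section 14.3.
2. Use all e-consenters as the denominator for study completion, survey completion and specimen return. Count kit non-return as non-completion.
3. Report the number reaching each step: asked, e-consent, Pre-Visit Survey, saliva and signature, result, phone triage, visit, end surveys. Show visits postponed for a positive test or triage separately from patient non-compliance.
4. Keep ease-of-testing ratings among those who tried the step, because people who never tried it cannot rate it. State how many gave no rating. Optionally, ask the relevant items at the withdrawal interview already in Section 5.4.2.

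The cost is protocol wording and one table. Consents are already recorded in REDCap (Section 12). The downside is a less favourable completion figure.

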5.2 Participant Exclusion Criteria

Participants would be excluded if they participated in the feasibility study previously or if they are unwilling to have their de-identified data made available to other researchers.

5.3 Strategies for Recruitment and Retention

Target Sample Size: 20 patients.

Target Sample Size by Gender, Race, Ethnicity, and Age: Study population will be drawn from patients at the Rutgers School of Dental Medicine. It is estimated that about ½ will be female, ½ male. All will be English speaking. Age range will be between 18 and 100 years of age. Racial and ethnicity background will be reflective of the respective populations at the Rutgers Schools of Dental Medicine with about 52% being African American and 33% Hispanic.

Study Population: The patient study population will be drawn from outpatient dental clinics located at Rutgers University School of Dental Medicine.

Inclusion of Women and Minorities and Individuals of All Ages:

Women: Women will be included in this study. Pregnant women are eligible to participate.

Minorities: Minorities will be included in this study.

Recruitment Strategies: Patients treated in the Rutgers School of Dental Medicine's Oral Medicine clinic will be recruited. If 20 patients cannot be recruited in the Oral Medicine clinic, recruitment will expand to the school's other clinics. It is not anticipated that there will be difficulties recruiting sufficient patients.

Retention: In order to minimize loss of study participants and/or incomplete data collection, the following activities will take place:

- The Research Clinical Director will work with the co-investigators responsible for recruiting subjects and completing surveys.
- Participants will receive compensation.

Compensation and Scheduled Payments: Patients who complete the protocol, including the post-visit survey will be provided \$100.

Additional Plans to Minimize Loss of Follow-up and Missing Data: The following will minimize loss of follow-up and/or missing data:

• When appropriate, REDCap survey data fields are set to "required".

REDCAP validation rules on data fields to limit responses to valid responses

5.4 Participant Withdrawal or Discontinuation from Study Procedures/Intervention

5.4.1 Reasons for Participant Withdrawal or Discontinuation from Study Procedures/Intervention

Participants are free to withdraw from participation in the study at any time upon request.

An investigator may discontinue an individual's participation in an intervention or withdraw an individual from the study if:

- The participant has a serious adverse event requiring hospitalization.
- Any clinical adverse event (AE), laboratory abnormality, or other medical condition or situation
 occurs such that continued participation in the study would not be in the best interest of the
 participant.
- The participant meets an exclusion criterion (either newly developed or not previously recognized) that precludes further study participation.

5.4.2 Handling of Participant Withdrawals from Study

Participants may withdraw participation consent at any time, either verbally or in writing. Participants who further withdraw their consent for the use of data already collected must do so in writing. The Research Clinical Director or co-investigators will interview the participant and document the withdrawal of consent using the Consent Withdrawn Received Form in the REDCap system. Participants who withdraw will not be replaced.

Documentation includes the date, the reason for participant withdrawal, as well as, the upload of any written withdrawal request. Upon withdrawal, all study procedures would cease, however, the participant would be offered continued care as part of the normal standard of care.

5.5 Premature Termination or Suspension of Study

This study may be suspended or prematurely terminated if there is sufficient reasonable cause. Written notification, documenting the reason for study suspension or termination, will be provided by the suspending or terminating party to [name] and the funding agency (NIDCR). The principal investigator will also promptly inform the IRB and NIDCR and will provide the reason(s) for the termination or suspension.

Circumstances that may warrant termination include, but are not limited to:

- Determination of unexpected, significant, or unacceptable risk to participants.
- Insufficient adherence to protocol requirements.
- Data that are not sufficiently complete and/or evaluable.
- Determination of futility.

6 STUDY SCHEDULE

6.1 Patient Subjects

The following is the schedule of events for patients participating in the study.

Visit	Day	LAB Subjects Activities Performed
2 Weeks Prior	Day -14 (+/- 7 days)	Potential subjects contacted to introduce and determine interest in the study Obtain electronic consent Complete Pre-Visit Patient Survey
1 Week Prior	Day -7 (+/- 5 days)	Obtain informed consent signatures Provide saliva specimen
Day Prior	Day -2 (+/- 3 days)	Perform Prior-Day Triage Survey Obtain test results and provide to patient subject
Visit	Day 1	Complete Start-of-Visit Survey Complete Start-of-Visit Triage Case Report (Provision of Dental Treatment - not part of research protocol) Complete End-of-Visit Survey Complete Patient Participation Questionnaire

6.2 Withdrawal Visit

Not applicable. If a subject withdraws early, there is no withdrawal visit.

6.3 Unscheduled Visit

Not applicable.

7 STUDY PROCEDURES/EVALUATIONS

As part of this study, COVID-19 triage case report will be completed, COVID-19 testing will be performed and perception and attitude surveys will be administered. During day 1, the dental visit, normal patient care will be provided to the patient subject.

For the purpose of this study, a COVID-19 positive result is not considered an adverse event though results of this test will be recorded.

Patient subjects who are COVID-19 antigen or viral positive or who triage positive without any preexisting medical condition, will not be seen for their scheduled dental visit. The subject will be referred to their physician for a definitive diagnosis and follow-up. The follow-up call will be made 1 week after (and 2 weeks after if necessary,) learning of the research study protocol call viral or antigen positive test results to record any confirmatory tests which were obtained based upon the advice of the worker's physician. The dental visit will be rescheduled once the subject has fully recovered. In the event of a dental emergency, care will be rendered via tele dentistry or referral to University Hospital Unit 1 (Oral and Maxillofacial Surgery/Dental Medicine Clinic) via University Hospital's Emergency Room.

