2 INTRODUCTION: BACKGROUND INFORMATION AND SCIENTIFIC RATIONALE

2.1 Background Information

Description of Problem:

The COVID-19 pandemic: COVID-19 has created serious concerns about the safety of patients and dental professionals as they return to a practice environment. The spread of this ubiquitous virus was first thought to be through droplets but soon it became clear that the virus could be spread by aerosols [5,6]. Many dental procedures require the mechanical preparation of hard and soft tissue using high speed handpieces which are water cooled and generate significant aerosolized sprays. The extent to which dentally-generated aerosols linger within operatories has not been clearly tested but it is certain that both dentists, dental assistants and hygienists will be exposed to significant aerosol sprays derived from patients' oral cavities [7]. As we learn more about COVID-19 and viral transmission we understand that infection and spread of the virus is due to the viral load (or dose) and the time of contact [8,9].

Uniqueness of Dental Practice: Unlike many procedures in medicine, dental/patient contact is eye to eye and the close proximity between patient and dental professionals is unavoidable [10]. Furthermore, a dental procedure can often take as long as 1 hour and prolonged close contact between dentist and patient is inevitable. Despite personal protective equipment (PPE) that includes N95 masks, face shields, gowns, and high-speed suction, viral spread from infected patients is unavoidable. This suggests that the only safe solution for maintaining the health and well-being of dental professionals in the time of COVID-19 is removing virus infected patients from their offices [11].

Waiting Rooms and Airflow: Obvious issues confronting dental practices have been discussed, however, waiting rooms with patients, bathrooms and passageways are all additional areas within offices that can be of concern. Further, the airflow in confined office spaces where patients can be waiting for 30 minutes or more can be hazardous if an asymptomatic but COVID-19 infected patient is in close proximity to a susceptible patient. Patients in a dental office can be at risk for infection that can have varied presentation and severity, and may be life threatening especially in patients with pre-existing conditions [21-23].

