Objective 1 – Dental health care personnel and patients feel safe in the dental office	Patient Safety and Comfort Survey asks patients their concerns about seeing their dentist and their perceptions about the value of different safety precautions. Willingness to Return for another Visit reflects a patient's comfort with safety practices employed by their dentist. Willingness to Refer Other Patients reflects a patient's or DHCW's safety of the dental practice.	Patients: Patient Safety and Comfort Survey 4 Items asking about concern on a 4 point Likert Scale – 1=not concerned at all, 2= mild concern 3=moderate concern, 4= severe concern 6 Items asking about safety on a 3 point scale – Not at All, Not Sure, yes 5 Items asking about Importance of safety practices on a 5 point Likert Scale – 1=extremely important, 2=important, 3 = Not important or unimportant, 4 = unimportant, 5 = very unimportant How safe to do feel coming to work? 5 Point Likert scale Patients – Willingness to Return for another Visit: How likely are you to return for another visit within the next 12 months? 5 Point Likert Scale Willingness to Refer Other Patients: How likely would you refer a family or friend to this dental office? 5 Point Likert Scale	Sense of Safety for Patients: Day prior to visit At end of visit Willingness to Refer Other Patients: LAB Patients - Day prior to visit All Patients - end of visit

3.2 Secondary Outcomes for Full Study (Data Collection is Being Performed to Determine Instrument Feasibility)

Objective	Brief Description/ Justification of Outcome Measure	Outcome Measured By	Time Frame
Objective 2: Determine the Efficiency and Effectiveness of: • Efficiency of Patient Triage Protocols • Effectiveness of LAB	Efficiency of Triage Protocols:	Efficiency of Triage Protocols: Time needed to complete triage survey Effectiveness of Triage Protocols Comparison of number of patients not able to have visit completed Comparison of Triage Survey to Medical History consistent with COVID-19 symptoms for DHCW Efficiency of Testing Protocols: Time and supplies needed to conduct LAB Effectiveness of Testing Protocols Number of patients not able to report for their patient visits LAB offices	Efficiency of Triage Protocols: LAB Patients: Start of visit Effectiveness of Triage Protocols Patients: End of visit Efficiency of Testing Protocols: Patients: End-of-Visit

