 - headache
 - loss of taste

[figure not shown]
- loss of smell
- sore throat
- congestion or runny nose
- nausea or vomiting
- diarrhea
- At the start of the Dental Visit
 - Undergo a COVID-19 triage screening in the office*
 - Screening includes symptom questions, temperature check, and pulse oximeter reading
- At the End of the Dental Visit
 - Complete two electronic surveys
 - Patient End-of-Visit Survey
 - Questions explore perceptions with testing preferences, PPE observed, environmental controls observed, concerns about returning to dental care, safety precautions valued, importance of triage and testing, likelihood of reporting symptoms, dentists role in COVID-19 testing and vaccinations
 - Patient Participation Survey
 - Questions explore perceptions related to study participation including survey and testing logistics

If any aspect of the COVID-19 triage screening is positive, appointment will be postponed and the participant will be referred to their primary care physician for further testing.

- A Positive screening by reporting one or more symptoms
- A positive temperature is considered greater than 100.4 degrees F
- A positive pulse oximeter is considered when the blood oxygen saturation level is below 95%

The results of the lab processed COVID-19 test will be reported to the Clinic Director or one of the coinvestigators by the lab prior to the scheduled dental visit. Results will be recorded in the *Testing Case Report* form in REDCap.

- If **POSITVE**: The Clinic Director or one of the co-investigators will communicate positive results to the participant upon receipt. Positive participants will be instructed to consult with their primary care provider for further testing.
- If NEGATIVE: The Clinic Director or one of the co-investigators will communicate negative results to
 the participant by phone on the day prior to the dental visit after the COVID-19 triage screening is
 performed.

Methods for Data Collection

REDCap will be used to collect and maintain all study data. For all surveys and case reports, the Research Clinical Director or co-investigator will enter data directly into REDCap. Surveys will be entered by the patient with the Clinical Director or co-investigator's assistance.

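### Section 7 leaves a test-negative, triage-positive participant with any preexisting condition outside the hold that Section 4 applies without exception

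*Combined protocol and SAP*

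**What the plan says.** Section 4 (Study Design) sets the triage rule: "If any aspect of the COVID-19 triage screening is positive, appointment will be postponed", and the participant is referred to primary care for further testing. One item is enough. For symptoms the definition is "A Positive screening by reporting one or more symptoms", for temperature it is a reading above 100.4 F, and for oximetry it is "A positive pulse oximeter is considered when the blood oxygen saturation level is below 95" percent. No exception is given.

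Section 7 (Study Procedures/Evaluations) restates the rule. It withholds the visit from participants with a positive test and from those "who triage positive without any preexisting medical condition, will not be seen for their scheduled dental visit". The next sentence refers these participants to their physician.

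No section defines a preexisting medical condition, requires it to explain the positive item, or says which section governs. Section 5.2 excludes only earlier participants and people who refuse data sharing, so patients with medical conditions can enrol.

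**The concern.** The two sections describe the same decision with different scope. Under Section 4, a participant with one positive triage item goes home and is referred. Under Section 7, the same participant drops out of the described hold if he or she has any medical condition on record, even one that has nothing to do with the finding.

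What is at stake is whether someone with a symptom, a fever or low saturation is treated that day. Section 7.1 lets the Clinical Director, a co-investigator or another staff member record triage, so the answer could depend on who screens and which section they follow. Seeing the participant would depart from Section 4, so it is also unclear whether it counts as a protocol deviation under Section 15.6. Triage is one of the procedures that this pilot is meant to try out before a larger study.

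**Working it through.** The plan has no figure to reproduce: Section 11.2 states that no sample size calculation was done. The check is a side-by-side reading, followed by simple arithmetic on timing and size.

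**Step 1. The two rules, case by case.**

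| Test | Triage | Preexisting condition | Section 4 | Section 7 |
|---|---|---|---|---|
| Positive | Any | Any | Result given, told to consult primary care; hold not stated unless triage is also positive | Held, referred |
| Negative | Positive | None | Held, referred | Held, referred |
| Negative | Positive | Yes | Held, referred | Not among those held or referred |
| Negative | Negative | Any | Not held | Not held |

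On triage, the sections part only in the third row. If the qualifier in Section 7 were read as attaching to the test-positive group as well, that row would not change.

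**Step 2. How current the test is.** Section 6.1 puts the saliva specimen at Day -7 +/- 5 days and the visit at Day 1. The window therefore runs from Day -7 - 5 = Day -12 to Day -7 + 5 = Day -2. The sample's age at the visit is 1 - (-2) = 3 to 1 - (-12) = 13 days, or 2 to 12 days if no Day 0 is counted. A negative result says little about status on the day. The telephone triage comes earlier and covers symptoms only. Temperature and oximetry are added at the visit.

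**Step 3. Size.** The target is 20 (Section 5.3). One participant is 1/20 = 5 percentage points of percent completing. That is an upper limit, reached only if the held visit is never rescheduled.

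The documents do not say how many participants will be test negative, triage positive and have a preexisting condition. Let p be that share, purely as an assumption, with participants independent. The expected number is 20p, and the chance of at least one is 1 - (1 - p)^20.

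| Assumed p | Expected number of 20 | Chance of at least one |
|---|---|---|
| 2% | 0.4 | 1 - 0.98^20 = 33% |
| 5% | 1 | 1 - 0.95^20 = 64% |
| 10% | 2 | 1 - 0.90^20 = 88% |
| 20% | 4 | 1 - 0.80^20 = 99% |

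The table shows only that the case could plausibly arise in a study this small. It does not estimate how often.

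**The case against.** The strongest reply is that the sections do not contradict each other. Section 7 lists people who will not be seen and is silent about the rest, so staff who hold every triage-positive participant comply with both. A reader might infer that the sections give opposite orders, but the text does not go that far: the exemption in Section 7 is implied. Even so, if everyone is held the qualifier does nothing, so its natural reading is as an exemption. Parts of the Section 7 paragraph also look carried over from another study, since it mentions a worker's physician and antigen results in a patient study that uses only saliva PCR. That supports treating Section 4 as the operative rule, and so supports removing the qualifier.

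Four further inferences are tempting, and the documents do not support them.

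- *That Section 4 would bar a participant with a chronic symptom for good.* The release condition, "The dental visit will be rescheduled once the subject has fully recovered", stands in the Section 7 paragraph, which on its own wording does not reach these participants. Section 4 says only that the visit is postponed. The route back is unspecified, but no permanent bar is stated.
- *That the unheld participants are the ones put in mortal danger.* Section 2.1 does say that infection "may be life threatening especially in patients with pre-existing conditions", but it is describing a susceptible person exposed to an infected one. Here the participant is the possible source, and the hold mainly protects others.
- *That a listed outcome of this study is distorted.* "Comparison of number of patients not able to have visit completed" appears in Section 3.2 as a full-study outcome, collected here to test instruments, and is not among the variables in Section 11.3.
- *That completion would fall by p under Section 4 and not at all under Section 7.* This needs everyone who is held to be lost and everyone else to complete. It is a worst case built on assumed shares.

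**Conclusion.** The point holds as a gap between two statements of a same-day safety rule. Section 4 is explicit and has no exception. Section 7, by implication, leaves a test-negative, triage-positive participant with any preexisting condition outside both the hold and the referral. Followed literally, it would allow a participant with fever and unrelated hypertension to be seen.

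The effect on results is limited. Section 4 states that "important outcomes include percent of patients willing to participate and percent completing the protocol", and only the second of these is touched, by at most 5 percentage points per affected participant at n = 20 and by less if visits are rescheduled. The number affected is unknown. The case for changing the text rests on consistent handling of possibly infectious participants more than on the percentages.

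**What to change.** Delete the five-word qualifier about preexisting conditions from Section 7, and state one rule in both sections, for example: *A participant with a positive SARS-CoV-2 test or any positive triage item is not seen at the scheduled visit and is referred to a physician. If the positive item is long-standing, the visit may be rescheduled after physician clearance.* Section 4 needs the clause on a positive test added, because it now describes only notification and advice to consult primary care.

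The cost is a few words and the IRB review that Section 14.2 requires for any amendment. No new data are collected. The downside is that a few participants with chronic symptoms will have visits delayed.

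If the sponsor did intend an exception, it should be limited to a positive item explained by a documented condition, should never cover fever or a positive test, and should be worded identically in both sections. That choice carries its own risk: an infected participant with, say, a chronic cough could be seen if a change goes unnoticed.
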